### 1.5 Time line of assessments and measurement

*Healthy donors:* After successful pre-screening over the phone, the potential donors will receive a copy of the consent form by mail or email. This will be discussed with the study coordinator over the phone. If the candidates agrees to participate, they will come to the hospital for a first visit, where screening questionnaires will be administered and screening blood work will be taken. In addition, the MINI semi-structured interview (130), Ham-A, MADRS and CR-RISC questionnaires will be administered. In order to perform an infectious disease screening, also stools and urine will be collected. If the donors pass the screening, they will be provided with a stool collection kit and forms for further assessments: food record, activity log, and environmental questionnaire. The donors will complete these forms during the week preceding their first stool donation. Three to five stool donations per donor will be collected within 2-4 weeks of successful screening (one donation is equal to 150gr of stools). These samples will be used for FMT. In addition, IM and metabolomics will be measured on one additional sample provided on first donation and frozen right after collection. Between each donation, donors have to fill-in a risk self-assessment and a diet screening form. Final screening will be performed two weeks after last donation, to ensure maximum safety of the samples collected.

For MTOP donors, bookend testing will also be done for AMDROs (MRSA, VRE, ESBL and CPO) occurs at a minimum of two-month intervals. Rescreening for other infectious diseases (stool, urine and blood) occurs at least every 6-months. FMT donations provided up to 2 weeks preceding re-screening are released only if re-screening is negative for AROs and all other screened infectious diseases. In addition, while donating stool, FMT donors complete self-screening questionnaires with every donation

for ongoing assessment for their medical health and risk of acquiring infectious diseases. If risk for infection is determined to be present on the questionnaire (e.g. travel to an endemic area for infectious disease), the donor is placed in a washout period prior to being rescreened to re-donate. Diabetes risk (HOMA-IR score), anthropometric measurements and mental health questionnaires are repeated at least every 12 months.

Morbidly obese patients: Patients will be approached if they have attended the information session and signed the psychosocial study consent where they agree to be contacted for future research studies. We will be targeting specifically those patients who decide not to go ahead with the bariatric surgery at this point in time (i.e. no follow-up arranged four weeks after the orientation session). Patients interested in our study calling us on their own initiative will be screened even if not previously evaluated by the Bariatric Clinic at TWH as long as they fulfil all other requirements. After a short phone screening, the patients receive a copy of the consent form, which will be discussed over the phone by the study coordinator. Then they will come to the hospital for the screening visit, where their medical history and medications are recorded and HOMA-IR will be measured to assess eligibility. Patients will be provided with forms for food records, activity log, environmental questionnaire, and a stool collection kit. If the patient lives far or specifically request it, he can have blood works done in an outside lab and kit will be mailed home. In this case medical history and medications are recorded over the phone. Once eligibility is confirmed depending on HOMA-IR measured at screening, patients will be called back for the baseline visit. The following will be assessed: bloodwork, anthropometric measurements, appetite rating, psychological MINI interview, depression, anxiety, and quality of life questionnaires. Then, an FMT appointment will be scheduled and patients will be randomized. Patients will collect stool samples adequate for a single transplant (150gr) before they start the bowel preparation for the colonoscopy. In the week before the stool sample is collected, they will complete the questionnaires provided at baseline. When they bring their stool sample to the hospital, completed forms will be collected, anthropometric measurements will be performed. Baseline measurements will be repeated at 1 and 3 months post FMT, except for quality of life, depression and anxiety scores.. After FMT patients are required to fill-in a symptoms diary to keep track of any AE possibly occurring. In addition, during the colonoscopy performed to administer FMT, mucosal samples will be taken from the rectum, the colon, and the terminal ileum to assess the mucosa-associated microbiome. Blood and colon secretions will be collected to evaluate the baseline immune status of the subject (infections existing prior to FMT) and colon secretions will be also stored for future research.

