### **1.2 Outcomes**

#### Main outcome: Insulin resistance (HOMA-IR)

Secondary outcomes: weight (absolute number, BMI, % change), appetite score, quality of life, anxiety and depression scores

*Other measurements:* HbA1c, C-peptide, IM in stools (composition and metagenome), amount of selected groups of microorganisms measured by qPCR, blood lipids, gut hormones, blood pressure, physical examination, food intake (energy and % of energy from fat, carbohydrates, protein, fiber intake (g/d)), physical activity (units/day), environmental questionnaire, stool and serum metabolomics.

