#### 1.6.3 Bloodwork

Sample collection and processing: Blood will be drawn in the morning after 12 hours fasting, based on the standard procedures at the University Health Network Laboratory Medicine Program. As insulin secretion is pulsatile, three samples will be taken at 5-min intervals, and the average of the three measurements will be calculated (165). Serum for metabolomics measurements will be collected into tubes without anticoagulant, placed on ice immediately, and centrifuged at 4°C, 2,800×g for 15 min. Serum will be aliquoted and frozen at -80°C until analysis. Samples for TNF- $\alpha$ , IL-6, and vitamin E will be collected in EDTA containing tubes, separated by centrifugation (910 × g, 10 min) and stored at -80°C until analysis. The same will be done for plasma endotoxin, but blood will be collected in pyrogen free heparin tubes (Monovette, Sarstedt, Nuernbrecht, Germany). Samples for hormone analysis will be collected in tubes containing protease inhibitors and other added chemicals described below, then separated by centrifugation (910 × g, 10 min) and stored at -80°C until analysis.

Analyses of standard blood biochemistry: The following standard tests will be performed at the Laboratory Medicine Program at the University Health Network:

Glucose: enzymatic hexokinase method (Bayer Advia 1650 Glucose package)

Insulin: microparticle enzyme immunoassay (MEIA) (Abbott Architect i2000)

Hemoglobin A1c: High-performance liquid chromatography (Variant)

C-peptide: chemiluminometric technology (Immulite 2000)

*Plasma lipids:* Triglycerides, total and high density lipoprotein (HDL) cholesterol are measured using the Abbot Architect. Low density lipoprotein (LDL) cholesterol is calculated as total cholesterol – HDL cholesterol.

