### 5.7.2 Statistical analysis plans

A descriptive summary of all measurements will first be compiled using appropriate graphical representations, and means, standard deviations and proportions will be calculated. Baseline characteristics of the randomized groups will be compared to ensure balance on the important variables (e.g. HOMA, BMI). Trajectory plots will be created to examine visually the changes over time.

The changes in the outcome variables of (HOMA-IR, weight, scores for appetite, quality of life, anxiety, and depression) within the two FTM groups (allogenic vs. autologous) will be compared using generalized linear mixed models (GLMM), where the within and between groups changes over time will be examined simultaneously. Factors with known influence on the outcomes will be examined for possible inclusion in our multivariate models as covariates, particularly if found imbalanced between the randomized groups. For patient drop-out, we will check missingness patterns and employ appropriate methods of handling missing data (181). The relationships between changes in outcomes and IM will first be investigated using correlation analysis (Spearman and Pearson correlation coefficients, Chi-square and Fischer exact tests as appropriate), and subsequently using methods for correlated data when considering multiple measures (incl. covariates, multiple time points, etc.). For the latter, we will employ generalized linear and nonlinear mixed models, as well as the generalized estimating equations approach. Goodness-of-fit tests will be applied for model diagnostics (182). In addition, principal component analysis (183), co-inertia analysis will be considered when investigating possible strategies for dimension reduction (where large numbers of variables may be correlated).

Statistical analyses will be performed using SAS 9.4 and R 3.2 (or subsequent versions as they become available), and all tests will be two-sided with a significance level of 5%. Where necessary, p-value adjustments for multiple testing (e.g. Holm's Bonferroni Step-down, Benjamini and Hochberg False Discovery Rate) will be employed (184).

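### The HOMA-IR analysis commits to no pre-FMT covariate, although two pre-randomization values are very likely collected; prespecify adjustment for baseline, with screening as an additional covariate of uncertain benefit

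*Combined protocol and SAP*

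**What the plan says.** HOMA-IR is the main outcome (section 1.2). Section 1.5 describes a screening visit at which "HOMA-IR will be measured to assess eligibility". Eligible patients return later: "Once eligibility is confirmed depending on HOMA-IR measured at screening, patients will be called back for the baseline visit". At that visit, "The following will be assessed: bloodwork, anthropometric measurements, appetite rating" and the psychological instruments. Randomization follows, and "Baseline measurements will be repeated at 1 and 3 months post FMT", with stated exceptions that do not include bloodwork. Entry requires HOMA-IR above 2.73 (section 1.3.1).

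Two details affect how comparable the values are. At screening, a patient who lives far away or asks for it may use another laboratory: "he can have blood works done in an outside lab". Section 1.6.3 says of blood draws that "three samples will be taken at 5-min intervals, and the average of the three measurements will be calculated", but does not say whether this covers outside laboratories.

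Section 5.7.2 sets the analysis: "The changes in the outcome variables of (HOMA-IR, weight, scores for appetite, quality of life, anxiety, and depression) within the two FTM groups" are compared with generalized linear mixed models. It does not say whether baseline enters as a covariate or as a repeated response, gives no scale for HOMA-IR, and does not mention the screening value. Covariates are left to an open clause, with emphasis on factors found to be imbalanced.

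**The concern.** The trial very likely holds two measurements of its main outcome taken before allocation, and the analysis text commits to adjusting for neither. Read literally, a comparison of changes subtracts a noisy baseline in full instead of weighting it by how well it predicts follow-up. That wastes precision when the correlation is moderate.

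The screening value is also a possible covariate. Three samples 5 minutes apart smooth pulsatile insulin secretion but not variation between days, which a value from another day can help to average out.

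Leaving the choice open also allows covariates for the main outcome to be selected after the data are seen.

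**Working it through.** **The plan's own figure.** Section 5.7.1 gives 18 per group randomized and 15 per group completing at 20% attrition: 15 × 1.2 = 18. Dividing instead gives 15/0.8 = 18.75, so 19; forward, 36 × 0.8 = 28.8 completers. The difference is trivial, and 30 completers are used below. No SD, correlation, effect size or power is stated for HOMA-IR.

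**Assumptions.** One follow-up time (no primary time point is stated); ln(HOMA-IR) normal with equal variance at each visit before selection; correlations *s* (screening–baseline), *b* (baseline–follow-up) and *a* (screening–follow-up); 0% or 30% of candidates screened out by the entry threshold.

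**Formulas without truncation, in units of the outcome variance.**
- Change score: 2(1 − b)
- Baseline as covariate: 1 − b²
- Proportional cut from adding screening: (a − sb)² / [(1 − s²)(1 − b²)]. With all correlations equal to r this is r²/(1 + r)².
- Finite-sample cost of k covariates at N = 30: (N − 3)/(N − 3 − k), that is 27/26 for one and 27/25 for two. The second covariate therefore costs 26/25, about 4%.

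**Worked example, all correlations 0.7.** Change: 2 × 0.3 = 0.60. Baseline covariate: 1 − 0.49 = 0.51. Cut from screening: 0.49/2.89 = 17.0%, leaving 0.51 × 0.830 = 0.424. Net increment: 1 − 0.830 × 26/25 = 13.6%. Both values against change: 1 − (0.424/0.60) × 27/25 = 23.7%.

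**Percentage reduction in treatment-effect variance, net of covariate cost.** For the 30% rows the variances and covariances after truncation were simulated and put into the same expressions (error a few tenths of a point). Simulated trials at 15 per arm agreed to within about 1 point.

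| s / b / a | Screened out | Both values vs change | Baseline alone vs change | Screening added to baseline |
|---|---|---|---|---|
| 0.6 / 0.6 / 0.6 | 0% | 25.8 | 16.9 | 10.6 |
| 0.6 / 0.6 / 0.6 | 30% | 25.8 | 21.6 | 5.4 |
| 0.7 / 0.7 / 0.7 | 0% | 23.7 | 11.7 | 13.6 |
| 0.7 / 0.7 / 0.7 | 30% | 23.8 | 16.9 | 8.4 |
| 0.75 / 0.75 / 0.75 | 0% | 22.9 | 9.1 | 15.1 |
| 0.75 / 0.75 / 0.75 | 30% | 22.8 | 14.2 | 10.0 |
| 0.7 / 0.7 / 0.6 | 0% | 12.5 | 11.7 | 0.8 |
| 0.7 / 0.7 / 0.6 | 30% | 11.8 | 12.5 | −0.7 |
| 0.7 / 0.7 / 0.49 (serial decay) | 0% | 8.2 | 11.7 | −4.0 |
| 0.7 / 0.7 / 0.49 (serial decay) | 30% | 4.6 | 8.3 | −4.0 |

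A smaller drop in *a* keeps some gain. At 0.7 / 0.7 / 0.63 the cut is 0.14²/0.51² = 7.5%, net 1 − 0.925 × 1.04 = 3.8%. At the other edge, serial decay from 0.75 with 30% screened out leaves about 2% for both values against change.

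**Outside-laboratory indicator.** A third covariate takes the cost relative to baseline alone from 26/25 to 26/24, about 8%. That would consume most of the gain in the middle rows.

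**The case against.** The strongest objection is that this is a preference, not an error. Section 5.7.1 calls the study a pilot. Section 5.7.2 leaves room for covariates and names HOMA among the variables to check for balance. A mixed model with a common baseline mean would already recover most of what baseline adjustment offers. This stands as far as severity goes. The text does not commit to such a model, however, and an open clause that leans on observed imbalance is not prespecification.

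Second, the two values are partly inferred: section 1.5 lists bloodwork at the baseline visit without naming HOMA-IR. That is a fair caveat. Since HOMA-IR is the main outcome and is analysed as change, a baseline-visit value is the natural reading, but the protocol should say so.

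Third, a reader might infer that the screening value is a free 10–17% cut in residual variance, worth 3 to 6 of 30 patients. The documents do not support that. It needs the older value to predict follow-up as well as the baseline value does. No correlation is given, and the interval between the two visits is not stated. It also omits the roughly 4% cost of the extra covariate. Truncation at 2.73 lowers the gain under equal correlations, and samples from outside laboratories may lower it further.

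**Conclusion.** The point holds as a minor improvement. Section 5.7.2 should commit to pre-FMT adjustment of HOMA-IR. Adjusting for both values did better than a plain change comparison in every scenario tried: roughly 5% to 26% less treatment-effect variance in the table, and about 2% at the edge. In most scenarios baseline adjustment supplies the larger part. The exceptions are equal correlations of 0.7 or 0.75 with nobody screened out.

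The separate contribution of the screening value is uncertain. It is about 5% to 15% net under equal correlations of 0.6 to 0.75, about nil to 4% when its correlation with follow-up is 0.07 to 0.10 lower (without truncation), and a loss of about 4% under serial decay. All of these figures rest on assumed correlations and an assumed share screened out.

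**What to change.** In 5.7.2, prespecify that the primary HOMA-IR model is on the log scale and adjusts for ln(HOMA-IR) from the baseline visit, with screening ln(HOMA-IR) as an additional covariate. State in 1.5 that the baseline bloodwork includes HOMA-IR.

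Never compute change from the screening value. It is selected to exceed 2.73, so regression to the mean would look like improvement within both groups. Do not add an outside-laboratory indicator by default, because it uses a further degree of freedom.

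The cost is two sentences and one degree of freedom for the screening term (about 4% of variance at 30 completers), with no new visit, sample or patient. The benefit will be smaller if many screening samples come from outside laboratories. If the sponsor expects the screening value to predict follow-up clearly less well than baseline, adjusting for baseline alone is a reasonable choice, provided it is also written down in advance.

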# **1 MATERIAL AND METHODS**

#### 1.1 Study Design

This will be a double-blind, placebo controlled randomized controlled trial. Morbidly obese men and women with IR who are eligible for bariatric surgery but did not perform such procedure will be approached. Those consenting will be randomly assigned to either allogenic FMT (prepared from stool donated by healthy lean donors with BMI <23 kg/m^2, matched for gender with the recipient) or autologous FMT (re-infusion of own collected feces; placebo). We plan to randomize 30 patients. Stool, blood, anthropometric measurements, questionnaires, quality of life, depression and anxiety will be assessed and will be collected before FMT and at 1 and 3 months post FMT. At baseline a physical examination will be performed, and will also be preformed if symptoms are present 3-months post-FMT . OM will be assessed before FMT and 3-months post FMT. Intestinal mucosa biopsies will be collected during colonoscopy for FMT administration as well as samples for safety.

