# 1.6.5 Psychological assessment

At baseline to all participants and 1 and 3 months after FMT for patients, we will also administer: *The Montgomery-Åsberg Depression Rating Scale (MADRS)*, a 10-item questionnaire which psychiatrists use to measure the severity of depressive episodes in patients with mood disorders (174); and *The Hamilton Anxiety Rating Scale (Ham-A)*, a clinician-rated evaluation whose purpose is to analyze the severity of anxiety. The scale is intended for adults, adolescents, and children and should take approximately ten to fifteen minutes to administer (175). Both questionnaires will be administered by the study coordinator.

To identify whether there are particular personality styles that make someone a good donor, we will also administer to the donors at baseline: the *Connor-Davidson Resilience scale (CD-RISC)*, which comprises of 25 items, each rated on a 5-point scale (0-4), with higher scores reflecting greater resilience (176).

*Quality of life:* This will be assessed using the RAND 36-Item Health Survey 1.0 (RAND SF-36), which has been developed for the Medical Outcomes Study (177). Patients will fill out the form at baseline and 3 months after FMT (*all psychiatric forms enclosed*).

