### **1.7 Statistical Considerations**

### 5.7.1 Sample size and power calculations

Our sample size is determined based on current literature, feasibility and the experience of team members, due to the pilot nature of the proposed study. Following common practice for this kind of studies (e.g. (179, 180)), we plan to recruit until we have randomized 36 eligible patients (18 per FMT

group). With a 20% attrition rate we assume that 15 patients per group will finish the intervention. This represents a greater sample size than the only previous FMT study on metabolic syndrome (26). We are confident that this sample size will allow us to investigate the stated aims.

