# 7 SAFETY EVALUATIONS AND ADVERSE EVENTS

# 7.1 Safety Evaluations

Timely and complete reporting of all adverse events (AE) assists in identifying any untoward medical occurrence thereby allowing:

- Continuous safety of study subjects
- A greater understanding of the overall safety profile of FMT.
- Appropriate modification of study protocols
- Improvements in study design or procedures
- Adherence to worldwide regulatory requirements

In this study, all subjects will be assessed according to their outcomes result (IR, HbA1c, weight, appetite). All parameters will be assessed again 1 and 3 months of treatment with FMT. In addition, a symptom diary will be kept for the 3 months to cover solicited and unsolicited AE. Monitoring process and safety assessments will be done by the study coordinator and the sponsor-investigator. The study coordinator will be in direct contact with the patients at each visit. The site investigator will monitor the safety data reported by the study coordinator. The bariatric surgery team will be consulted, in case their expert opinion is needed. As safety assessment, adverse events will be assessed at each visit. Patients may also call the study team at any time in case of concerns.

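### The time line section drops quality of life, depression and anxiety from the 1- and 3-month visits, against the design and methods sections, which also disagree with each other on 1-month quality of life

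*Combined protocol and SAP*

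**What the plan says.** Three sections of the combined protocol and SAP set assessment times for quality of life (RAND SF-36), depression (MADRS) and anxiety (Ham-A).

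- **1.1 Study Design** puts all three at baseline and at both later visits: "quality of life, depression and anxiety will be assessed and will be collected before FMT and at 1 and 3 months post FMT".
- **1.5 Time line of assessments and measurement** lists all three at the baseline visit and then says: "Baseline measurements will be repeated at 1 and 3 months post FMT, except for quality of life, depression and anxiety scores". It names no other time after FMT for them.
- **1.6.5 Psychological assessment** introduces MADRS and Ham-A with "At baseline to all participants and 1 and 3 months after FMT for patients, we will also administer". For the RAND SF-36 it says: "Patients will fill out the form at baseline and 3 months after FMT".

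The scales are not incidental. Section 1.2 lists the secondary outcomes as weight followed by "appetite score, quality of life, anxiety and depression scores". Section 5.7.2 plans a mixed-model comparison of the two groups on "The changes in the outcome variables of (HOMA-IR, weight, scores for appetite, quality of life, anxiety, and depression) within the two FTM groups".

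**The concern.** Section 1.5 is where site staff would look to see what is done at each visit. If they follow it as written, none of the three scales is administered after FMT. Each would then have a baseline value and nothing to compare it with, so the change analysis in 5.7.2 would be impossible for three of the five secondary outcomes.

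A less extreme outcome is also possible. If different sections were followed for different patients or visits, scores would be missing at some visits for reasons unrelated to the patient, in a trial that expects 15 completers per group. A score not taken at its visit cannot be recovered afterwards.

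The gap between 1.1 and 1.6.5 is smaller. It leaves open whether the quality-of-life model has one post-baseline time point or two.

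**Working it through.** The plan gives no figure to reproduce here. The check sets the schedules side by side and counts the scores each would produce.

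**Step 1. Post-FMT assessments per patient**

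| Section | Quality of life | Depression | Anxiety | Total |
|---|---|---|---|---|
| 1.1 | 2 (1 and 3 months) | 2 | 2 | 6 |
| 1.6.5 | 1 (3 months) | 2 | 2 | 5 |
| 1.5, literal | 0 | 0 | 0 | 0 |

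Sections 1.1 and 1.6.5 agree on depression and anxiety and differ only on quality of life at 1 month. Section 1.5 differs from both on every scale.

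**Step 2. Can a milder reading of 1.5 remove the conflict?** The sentence ends in a double full stop, so a qualifier may have been lost. Three readings were tried.

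- *Not at both visits.* This allows at most one post-FMT assessment per scale. It could fit quality of life in 1.6.5, but not depression and anxiety, which 1.6.5 places at both visits. It fits 1.1 on no scale.
- *Excepted at 1 month only.* This is a special case of the first reading and fails for the same reasons.
- *These scales follow their own schedule in 1.6.5.* The exception would then be pointless for depression and anxiety, because 1.6.5 gives them the same 1- and 3-month schedule from which 1.5 excepts them.

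No reading brings 1.5 into agreement with both other sections, and none touches the difference between 1.1 and 1.6.5.

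**Step 3. Does another section settle it?** Section 7.1 says parameters are reassessed at 1 and 3 months, but its list reads "all subjects will be assessed according to their outcomes result (IR, HbA1c, weight, appetite" and includes none of the three scales. Sections 1.2 and 5.7.2 show that post-FMT values are needed, but not at which visits.

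**Step 4. Number of scores at stake.** Section 5.7.1 gives the number of completers: "With a 20% attrition rate we assume that 15 patients per group will finish the intervention". That is 2 × 15 = 30. Post-FMT scores = (assessments per patient, summed over the three scales) × patients.

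| Schedule | 30 completers | 36 patients, no attrition |
|---|---|---|
| 1.1 | (2+2+2) × 30 = 180 | 6 × 36 = 216 |
| 1.6.5 | (1+2+2) × 30 = 150 | 5 × 36 = 180 |
| 1.5, not at both visits (maximum) | (1+1+1) × 30 = 90 | 3 × 36 = 108 |
| 1.5, literal | 0 × 30 = 0 | 0 × 36 = 0 |

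With 30 completers, 1.1 and 1.6.5 differ by 180 − 150 = 30 scores, all of them quality of life at 1 month. Even the milder reading of 1.5 falls 150 − 90 = 60 short of 1.6.5: 30 depression and 30 anxiety scores.

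The base of 30 is the plan's own. A 20% loss from 36 would leave 36 × 0.8 = 28.8, slightly fewer. This scales the totals but does not change the pattern.

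**The case against.** The strongest reply is that nobody could intend the literal reading. Section 1.6.5 is the instrument-specific text and gives a complete schedule, 1.2 makes the scales outcomes, and 5.7.2 analyses their change. The double full stop suggests an editing remnant. MADRS and Ham-A are assigned to the study coordinator, who also sees patients at each visit, so practice that varies between patients is unlikely. Section 1.1 is a one-sentence overview and weak evidence against a specific methods statement. The scales are secondary outcomes in a self-described pilot, and counting scores does not measure a loss of precision or power.

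Much of this is fair. The zero is a worst case, inconsistent practice is a possibility rather than something the documents show, and the 1-month quality-of-life point taken alone is a clarification. The totals show how many data points depend on the wording and nothing more.

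The reply does not remove the contradiction. That 1.5 is probably a slip is a reason to correct it: it is an explicit instruction in the section that governs visits, and nothing in the protocol says that 1.6.5 prevails. A mixed model can work with one or two post-baseline visits, but not with none.

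**Conclusion.** The concern holds. Section 1.5 contradicts 1.1 and 1.6.5 on all three scales if read literally, and under the milder readings still contradicts 1.1 on all three and 1.6.5 on depression and anxiety. Separately, 1.1 and 1.6.5 disagree on quality of life at 1 month, and the documents do not show which is intended.

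At worst, three of the five secondary outcomes have no post-FMT data: 0 scores against the 150 or 180 promised elsewhere for 30 completers. That result assumes that staff follow 1.5 to the letter. The contradiction itself needs no assumption. The main outcome, weight and appetite are unaffected. Because the loss would be irreversible and the correction costs a few sentences, the sections should be reconciled before follow-up visits are run from them.

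**What to change.** 1. **Section 1.5:** replace the exception with an explicit schedule for each scale. Deleting the exception alone is not enough, because the remaining sentence would place quality of life at 1 month and create a new conflict with 1.6.5.
2. **MADRS and Ham-A:** baseline, 1 month and 3 months, as 1.1 and 1.6.5 already agree.
3. **RAND SF-36:** baseline and 3 months as the working draft, following the instrument-specific text in 1.6.5. The sponsor should confirm whether the 1-month assessment in 1.1 is to be kept. If it is dropped, amend 1.1; if it is kept, amend 1.6.5. The schedule should then be identical in 1.1, 1.5 and 1.6.5.
4. **Section 5.7.2:** add a sentence naming the time points that enter the model for each outcome. This is a useful clarification rather than the core of the correction, and the model itself need not change.

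The cost is wording in three places: 1.5, 5.7.2, and either 1.1 or 1.6.5. No visit or instrument is added, since every assessment is already promised in 1.1 or 1.6.5.
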